The SAPS will be performed at screening and four weeks later at baseline to identify subjects with persistence of sufficient delusional severity to enter the study. The clinical assessment battery will be comprised of the Psychotic Symptom Rating Scale (PSYRATS), Brief Psychiatric Rating Scale (BPRS), Scale for Assessment of Negative Symptoms (SANS), Calgary Depression Scale for Schizophrenia (CDSS), Clinical Global Impression (CGI) and Heinrich's Quality of Life Scale (QLS). We are using this broad battery of tests to compare treatment groups at baseline and to allow exploratory analyses to help us understand the effects of DCS on our primary outcomes and to guide selection of outcome measures for future studies. The clinical battery will be administered at baseline and weeks 4, 8, 12, 24, and, in most subjects,

Study #:S12-02991

36. In addition, the Delusion Subscale of the PSYRATS will be administered at weeks 2, 3, 6 & 10 to assess the time course of DCS effects on delusions. Ratings will be performed prior to the DCS/CBT session each week. Additionally, the Drug and Alcohol Questionnaire and the Pittsburgh Sleep Quality Index will be performed at baseline. Assessment of cognitive functioning will be measured by the MATRICS battery at baseline only since we have found no effect of daily or weekly DCS administration on this and similar cognitive batteries in four randomized controlled trials. The SAFTEE will be administered at weeks 3, 4, 8, and 12. The SAFTEE is a self-report measure on which the participant rates the severity of 55 side effects on a 4 point Likert Type scale. The scale also asks the participant to furnish an overall rating on the severity of all side effects. Participants will be followed regardless of whether they remain on study drug or comply with CBT sessions to permit an unbiased causal estimate of D-cycloserine treatment efficacy under the intention-to-treat principle. Additionally, a per protocol analysis will be performed using data only from subjects who have substantially complied with the protocol.

The Psychotic Symptom Rating Scale (PSYRATS) (46): The PSYRATS is a well-validated 17 item, 5 point likert scale which contains 6 items that characterize delusions according to 1.) Amount and duration of preoccupation, 2.) Conviction, 3.) Amount and intensity of distress, and 4.) Disruption to life. We selected the PSYRATS because it frequently has been used in CBT studies, because we previously demonstrated that it captured response to DCS augmentation of CBT, and, unlike the Positive and Negative Syndrome Scale (PANSS), Scale for Assessment of Psychotic Symptoms (SAPS) and the Brief Psychiatric Rating Scale (BPRS), it rates subjective distress and the degree to which delusions disrupt life, both of which are important targets of CBT. Factor analysis has revealed three dimensions (47): preoccupation, conviction and distress/life disruption, with modest correlation between preoccupation and conviction ($r=0.28$) (46). We will use the Delusion Subscale total score as our primary outcome measure and, as an exploratory analysis, we will look at the three domains to further characterize DCS effects.

Assessment of memory consolidation: The Logical Memory Test of the Wechsler Memory Scale (WMS-III) will be used to measure memory consolidation, as in our pilot trial (30). Subjects will be administered Story A one week prior to baseline and will be tested on immediate item and thematic recall. One week later, at baseline they will be tested on 7-day delayed thematic recall. At week 3, one hour after administration of study drug, (immediately before the CBT session), participants will be administered story B, which will be tested for delayed thematic recall immediately prior to administration of study drug the following week. This will allow us to assess the effect of the first dose of DCS on memory consolidation following the same protocol that we used successfully in a previous study (30). The 2-week gap between administration of story A and story B will minimize potential interference between tests.

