 - b. Persistence Hypothesis: DCS improvement of delusions compared to placebo will persist at 3 and 6 month follow-up as defined as maintenance of a 20% or greater reduction in the PSYRATS Delusions Subscale total score from baseline.

Tertiary

3. Identify mediators of delusional response to DCS.
 - a. Memory Consolidation Hypothesis: Change in 7-day thematic recall on the Logical Memory Test after the first dose of DCS will predict improvement on the PSYRATS Delusions Subscale total score at 12 weeks.
 - b. Cognitive Flexibility Hypothesis: Change in the number of alternative beliefs generated during the first compared to the second administration of the Alternative Beliefs exercise in the DCS group will predict improvement of the PSYRATS Delusions Subscale total score at 12 weeks.
4. Identify neural differences in patients compared to age-matched healthy control population.
 - a. Network connectivity hypothesis: Decreased connectivity between the hippocampus and prefrontal cortex in patients at rest and during encoding of stories

Study #:S12-02991

and images, DCS enhancement of connectivity.

b. Memory Hypothesis: Patient impairment of network connectivity will predict performance on immediate and 1-week delay memory relative to healthy controls

Background Significance:

Public Health Significance: Delusions remain a serious public health problem, with persistent antipsychotic-resistant delusions present in approximately 30% of schizophrenia patients. In addition, most patients experience intermittent psychotic relapse associated with major disruptions in rehabilitation and recovery. Persecutory delusions are associated with great psychological distress to patients and family members, whereas other forms of delusions commonly result in social and vocational disability, incarceration, and can result in harm to self or others.

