Summary of Innovation: This study builds upon recent findings in translational neuroscience supporting a role for deficits in thalamo-cortical connections and memory consolidation in the persistence of delusions and follows from recent data demonstrating that, at low concentrations, DCS is a highly potent and selective agonist at a subpopulation of NMDA receptors involved in memory consolidation. This subgroup of NMDA receptors appears to be specifically down-regulated in schizophrenia. Although DCS has been well-established as an effective augmenter of CBT for anxiety disorders, this study (and our pilot trial) represents the first application of this approach for delusions. We are also the first group (MGH) to examine memory consolidation and fear extinction in schizophrenia and the first to examine measures of memory consolidation and cognitive flexibility as potential mediators of DCS effects when combined with CBT. If positive, this study could lead to an entirely novel approach for the treatment of delusions.

Characteristics of the Research Population:

Number of Subjects: Total planned enrollment of randomized subjects for the study is 64 subjects since this will ensure sufficient statistical power to detect any effects. In order to achieve adequate enrollment, we will consent and screen up to 140 individuals which will allow for a 40% screen failure rate. 77 participants will be enrolled for a total of 44 randomized subjects at NYU, and 33 participants will be consented at Sheppard Pratt for a total of 20 randomized participants. Additionally, 30 age and gender matched healthy subjects will be consented for the MRI portion of the study in order to enroll 15 healthy subjects.

The recruitment of 15 healthy subjects will be used as a comparison group against schizophrenia patients when analyzing fMRI scans. Due to the innovative nature of the tasks patients are doing while in the scanner, the addition of healthy participants will allow us to better identify any neural differences in these two groups, specifically to see if D-cycloserine enhances connectivity in specific neural regions.

Age of Subjects: Individuals between the ages of 18-68 will be included. Children below age 18 will not be included in this study. Schizophrenia is primarily an illness of adulthood and we would first like to explore the effectiveness of this intervention on adults. Healthy controls will have no history of mental illness.

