Rationale for DCS Dosing: DCS was developed as an antibiotic and used at doses of 500-2000 mg/d for tuberculosis but is now rarely used due to psychiatric and neurological side effects (activation, confusion and seizures) at these doses. It has a serum half-life of 4 hours and maximum CSF concentrations equal to 80% of serum concentrations are achieved 2 hours after oral dosing (39). It has been well-tolerated and effective at single weekly doses of 50 to 500 mg/d in subjects with anxiety disorders (40). A recent review found that DCS doses of 50-100 mg were most effective in anxiety disorder subjects provided they were administered within one hour of CBT sessions (25). In a placebo-controlled dose finding trial, we found that daily dosing with DCS 50 mg for two weeks improved negative symptoms and working memory, whereas doses of 15 mg and 250 mg daily were ineffective (41). In three trials in which DCS 50 mg was administered as a single dose or once-weekly, we found enhancement of memory and enhancement of CBT efficacy for delusions without adverse effects (32, 42). At doses above 100 mg/d DCS has been associated with worsening of psychosis in two studies (43, 44) and in

Study #:S12-02991

a study of DCS 50 mg daily we observed worsening of delusions in one subject who achieved unusually high serum concentrations (45). Recent studies by Dravid and colleagues (17)

suggest that at low concentrations DCS acts as a high-potency selective agonist at NR2C-containing NMDA receptors which mediate memory consolidation; at higher concentrations DCS binds as a partial agonist at NR2A and NR2B subunits which may contribute to worsening of psychosis in some patients. Taken together, it appears that the optimal dose of DCS is approximately 50 mg; unlike subjects with anxiety disorders, schizophrenia subjects appear at risk for worsening of psychosis at higher doses. Given the extensive prior experience and the risk that higher doses will worsen psychosis, we do not believe a dose finding trial is necessary and do not believe exposing schizophrenia subjects to a higher dose is justified. In addition, DCS serum concentrations will not be informative in this once-weekly dosing trial since steady state will not be achieved and given the variability in Tmax.

IND Exemption:

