MRI images will be performed at the NYU site only. Two MRIs without contrast will be performed as part of the study, before and after the first administration of D-Cycloserine. Specifically, each of these will consist of the acquisition of a high-resolution MPRAGE scan that will be motion corrected (Siemens 3 T Skyra, resolution 1 mm³, slices = 192, TR = 23000 ms, TE = 2.96 ms, FA = 9°, FOV = 256mm) to create a single image volume with high contrast-to-noise, a T2-weighted anatomical image (1mm³, slices = 192, TR = 3200 ms, TE = 422 ms, FOV = 256mm). In addition, several scans will be acquired that will allow us to determine whether D-cycloserine-induced changes in cortical thickness and hippocampal volume in the patients are accompanied by related changes in connectivity of the frontal cortex and hippocampus (measured using diffusion tensor imaging (DTI), and resting-state, functional connectivity MRI (FcMRI)). Thus, one 6 minute, 18 second long fcMRI scan (TR = 2500 msec; TE = 30 msec; flip angle = 90; slices = 46, 3 mm³ voxel size), and one approximately 9 minute DTI scan (TR/TE=7000/82 ms, b=700 s mm⁻², 256x256 mm FOV, 128x128 matrix, 2 mm slice thickness, 10 T2 + 60 DWI) will be acquired. We will also collect fMRI data to examine whether d-cycloserine has effects on the function of hippocampal subfields. Subjects will look at stimuli presented via projector on a screen placed at the back of the bore. They will be instructed to indicate, using a button response box, how the stimuli relate to categories and/or one another. During fMRI, subjects will complete 5 blocks of 90 trials, during which time we will collect Blood Oxygen Dependent Level (BOLD) data (5 x 184 x 19 slices, TR = 2000 ms, TE = 30 ms, Flip Angle = 70°). This task will take approximately 30 min. During anatomical scans, subjects will be asked to merely keep their eyes open and relax. During fMRI and FcMRI subjects will be asked to view images and make choices (former) and rest with their eyes open and focused loosely on the screen. The entire scan will take approximately 1 ½ to 2 hours.

Assessments:

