Healthy subjects will be consented and screened for eligibility. Then, participants will perform a logical memory test, immediate recall test, and 25 minute recall. Participants will also perform a verbal fluency test. KVLT-R and BVMT-R and Rey Complex Figure test (RCFT).

Visit 2

Healthy subjects will perform the 1 week retrieval for the logical memory task, be given instructions for the scan test, and undergo the first set of MRI and fMRI scans.

Visit 3

Healthy subjects will complete the second set of MRI and fMRI scans.

Visit 4

Subjects will perform a memory recall task from the fMRI scan on visit 3 and a story segmentation task based on the fMRI scan on visit 2..

Data Analysis and Data Monitoring

Analysis Plan:

Primary: Between treatment differences in PSYRATS Delusions Subscale

Mean effects in week 12. The mean effect of DCS + CBT compared to Placebo + CBT on delusions will be tested using a linear mixed model repeated measures (MMRM) analysis of modified PSYRATS with fixed terms for study visit, DCS/Placebo treatment group and visit by treatment interaction. The model will include random subject effects. Baseline PSYRATS will be included in the model together with a baseline by treatment interaction term. The MMRM will assume a means model, an unstructured covariance matrix and parameter estimation will be based on restricted maximum likelihood. Because of the potential for failure of model convergence due to the requirement of a large number of interaction terms, only a few other covariates will be considered. These may include baseline SANS total score and demographic variables including age and gender, which may be predictive of outcome. To test treatment difference in change from baseline in PSYRATS, we will use a-pairwise contrast on the terms for DCS treatment by visit interaction. To examine differential treatment effects at each CBT week if there is significant interaction, we will perform tests of simple main effects. A significantly larger 12-week decline in mean PSYRATS total score for subjects receiving DSC supports the

Study #:S12-02991

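### The DCS part of aim 4a names only healthy controls, who get no study drug, as its comparison; no DCS-versus-placebo imaging contrast is written

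*Combined protocol and SAP*

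**What the plan says.** Tertiary aim 4 is headed "Identify neural differences in patients compared to age-matched healthy control population". Hypothesis 4a, under that heading, first predicts lower hippocampal-prefrontal connectivity in patients at rest and during encoding of stories "and images, DCS enhancement of connectivity". No placebo comparison is named.

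The Number of Subjects section states: "The recruitment of 15 healthy subjects will be used as a comparison group against schizophrenia patients when analyzing fMRI scans". It gives the reason as identifying neural differences between these two groups, "specifically to see if D-cycloserine enhances connectivity in specific neural regions".

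Study Visits for Healthy Subjects lists four visits. Scans take place at visits 2 and 3 ("Healthy subjects will complete the second set of MRI and fMRI scans"), and no study drug appears at any visit.

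The MRI section limits imaging to NYU and places the two patient scans "before and after the first administration of D-Cycloserine". It speaks of DCS-induced changes in the patients, without naming an arm, a visit or an interval after the dose.

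The Analysis Plan covers the primary, secondary and mediator analyses. It has no imaging analysis. Elsewhere, the protocol randomizes patients 1:1 to DCS or placebo and plans 44 randomized patients at NYU.

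**The concern.** A hypothesis that a drug changes connectivity needs a comparison that differs only in the drug. The two comparisons that the text offers do not.

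- **Patients against healthy controls.** A difference at one scan reflects illness. A difference in change from scan 1 to scan 2 reflects DCS plus anything else that makes patients change differently: repeat scanning in illness, the CBT sessions between scans, and expectation.
- **Before against after in patients.** This carries all of those influences plus the ordinary retest effect. It is also undefined for half the sample, because a placebo patient never has a first DCS administration.

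An analyst following the text could therefore report a DCS effect on connectivity that has nothing to do with DCS, or miss one that is masked by an opposing change. The finding would be offered as mechanistic support for the treatment, although randomization provides a clean contrast. The stakes are limited to one half of one tertiary hypothesis; the PSYRATS results are not affected.

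**Working it through.** **Inputs.** 44 randomized NYU patients and 15 healthy subjects (Number of Subjects); 1:1 allocation (Estimation of statistical power); two-sided 0.05 (Analysis Plan, borrowed from the clinical analyses). Assumptions: all 44 are scanned, allocation within NYU is even (44/2 = 22 per arm), and non-DCS shifts are 0.2 to 0.8 SD of the scan-to-scan change.

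**The plan's own figure.** There is no imaging sample-size or power figure to reproduce. As a check on the formula, the primary-outcome claim (60 evaluable, 1:1, effect size 0.8, power above 85%) gives 87.3% by the normal approximation and 86.1% by the noncentral t. It reproduces.

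**What each comparison contains.** Write the expected scan-1-to-scan-2 change as a sum of parts:

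- DCS patients: retest + illness-related change + CBT and expectation + DCS
- Placebo patients: retest + illness-related change + CBT and expectation
- Healthy controls: retest

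DCS patients minus controls leaves illness-related change, CBT, expectation and DCS. Before/after in DCS patients leaves all four parts. Only DCS minus placebo leaves DCS alone.

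**How often a null DCS effect would look real.** Set the true DCS effect to 0 and let δ be the non-DCS shift in SD units. For two groups the noncentrality is δ/√(1/n₁ + 1/n₂); for before/after it is δ√n. The probability is that of exceeding the two-sided 0.05 critical t in the direction of the shift (the opposite tail adds at most 0.6 percentage points).

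Worked case, 22 against 15 with δ = 0.4: √(1/22 + 1/15) = 0.335; noncentrality 0.4/0.335 = 1.19; critical t on 35 df = 2.03; probability 21%.

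| Comparison | δ = 0.2 | 0.4 | 0.6 | 0.8 |
|---|---|---|---|---|
| 22 DCS patients vs 15 controls | 8% | 21% | 41% | 64% |
| All 44 patients vs 15 controls | 10% | 26% | 51% | 75% |
| Before/after, 22 DCS patients | 14% | 43% | 77% | 95% |
| 22 DCS vs 22 placebo | 5% | 5% | 5% | 5% |

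In the before/after row, δ is the patients' whole non-DCS change, retest included. In the last row the shift is common to both arms and cancels.

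**What the randomized contrast can detect.** Normal approximation at 80% power: (1.96 + 0.84) × √(2/22) = 2.80 × 0.3015 = 0.84 SD. With the noncentral t it is 0.86 SD. Power at 0.8 SD is 74%. If only 18 or 15 per arm give usable scans (assumed), the detectable effect is 0.96 or 1.06 SD.

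**When scan 2 probably falls.** In Payment for Participation, the $30 visits 3, 7, 11 and 15 line up with the full batteries at baseline and weeks 4, 8 and 12, so visit number minus 3 gives the week. Visit 6 is then about week 3, the session of the first possible DCS dose. Its $60 fits a $10 visit plus a $50 scan, and the table closes: 8×10 + 7×30 + 50 + 60 = 400. This is inference; no section states it.

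**The case against.** The best defence is that the trial is placebo-controlled, randomized and blinded, so a DCS-versus-placebo reading of any DCS hypothesis is natural. The Number of Subjects section describes healthy subjects as an addition and does not say that they replace the placebo arm. The MRI section does place the DCS question within patients. The disputed clause sits in a recruitment paragraph, not in an analysis specification.

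Part of this stands. A reader might infer that the design cannot show a DCS effect on connectivity. The documents do not support that: if both arms are scanned, the data allow the right test. But the contrast cannot be taken as implied. The one comparison group that is named is the wrong one, the Analysis Plan is silent on imaging, and the plan elsewhere does restrict a mechanistic analysis (memory consolidation) to subjects randomized to DCS.

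Stronger readings on timing are also tempting and should not be made:

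- **That scan 2 may fall at any time after the dose.** The visit and hour are unstated, but the payment table points to visit 6.
- **That the 4-hour half-life shows how much drug is left at the scan.** Simple decay from dosing ignores absorption. Rationale for DCS Dosing says "maximum CSF concentrations equal to 80% of serum concentrations are achieved 2 hours after oral dosing", so 2 hours is a peak for a brain measure.
- **That a scan within 24 hours is too early.** The protocol's statements on a 24-hour delay concern performance, not connectivity.
- **That the scan collides with the 1-hour interval between dose and session.** The length is given ("The entire scan will take approximately 1 ½ to 2 hours"), but no section puts the scan in that interval.

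Unstated timing that is the same in both arms would not bias a randomized contrast.

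**Conclusion.** The concern holds as a defect in the stated comparison, not in the design. For the hypothesis that DCS enhances connectivity, the text offers healthy controls without study drug or an uncontrolled before/after change. Neither isolates DCS, and the randomized contrast that would is not written.

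Under assumed non-DCS shifts of 0.4 to 0.8 SD, the false-positive rate is 21% to 64% against controls and 43% to 95% before/after, compared with 5% for DCS versus placebo. The shifts are illustrative, because the documents give no imaging variability. That healthy subjects are undrugged is read from the absence of drug in their visit list. That placebo patients are scanned is implied by the text but not stated.

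The change should be made, in proportion to a tertiary aim. Healthy controls remain the right comparator for the patient-versus-control parts of aim 4.

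**What to change.** 1. In the Analysis Plan, state the DCS test of aim 4a as DCS versus placebo among randomized NYU patients, on scan-2 connectivity adjusted for scan 1.
2. Keep healthy controls for the patient-versus-control parts of 4a and for 4b, and correct the Number of Subjects sentence that says they show the DCS effect.
3. State that both arms are scanned.
4. Replace the MRI section's reference to the first DCS administration with the session-3 study-drug administration, DCS or placebo, and fix the same visit and interval after it in both arms. Session 3 must be named because the CBT/DCS Protocol gives every patient placebo before sessions 1 and 2. If visit 6 is intended, say so.
5. Acknowledge the precision: about 22 per arm and a detectable effect of about 0.86 SD at 80% power, under the assumptions above.

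The cost is wording and slightly less freedom in scheduling scan 2. No extra scans or subjects are needed if both arms are already scanned; if only DCS patients were to be scanned, placebo-arm scans would have to be added. The contrast has only modest precision, and a null result should be reported with its confidence interval.

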CBT/DCS Protocol: Individual manualized CBT sessions will last 50 minutes and will be offered weekly for 12 weeks. The first two sessions will focus on engagement, characterization of delusions, and formulation of a treatment plan. Sessions 3 & 4 will consist of an alternative beliefs exercise as employed in our pilot trial in which subjects are trained to produce as many explanations as possible for a series of benign social vignettes (e.g., a taxi driver is staring at you), culminating with their own delusional belief (32). The exercise is structured with a fixed set of vignettes which allows us to record the number of alternative explanations generated by the subject during the exercise as a measure of cognitive flexibility. The remaining 8 sessions will include exploration of antecedents of delusional beliefs, development of a normalizing rationale, cognitive restructuring, testing of explanatory models, and review and consolidation. Study drug (DCS 50 mg or matching placebo) will be administered orally, 1 hour prior to sessions 3-12. Placebo will be administered prior to sessions 1 & 2. DCS and matching placebo capsules will be formulated by the NYUMC research pharmacy.

If a subject misses three consecutive study visits and corresponding CBT sessions, he/she will be withdrawn from the study. These missed visits and sessions may compromise the integrity of the study data and adversely affect the therapeutic alliance which is important in the CBT treatment.

CBT will be provided by [name], a PhD psychologist who trained under [name] at MGH using manualized CBT protocols. A second PhD level therapist may be added and will have at least one year of intensive CBT training and experience working with psychosis. To ensure that there will be no effect due to CBT therapist, balance will be maintained such that each therapist will be assigned to the same number of subjects assigned to DCS as to placebo. This will be accomplished by a statistician independent of the study. Before initiation of the study, training will be provided by [name] who will also provide weekly supervision by video-

Study #:S12-02991

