effectiveness of DCS. The probability of a type one error, the size of the test, will be controlled at 0.05, and all tests will be two-tailed. Overall alpha will be maintained at 0.05 for analyses of primary parameters. No adjustments will be made for multiplicity among secondary parameters analyzed. *Missing data*: The analysis will utilize the intention-to-treat principle. All randomized subjects, both completers and non-completers, will be included in the analysis without imputation. Estimates will be unbiased if follow-up data that are missing are "missing at random" conditional on the observed data and model assumptions.

Secondary: Characterizing onset and duration of effectiveness of DCS

a and b. Testing equality of the distributions of onset and duration. Onset is defined as the first week at which the criterion for response is met that lasts at least to the final week of the treatment period. Kaplan-Meier estimates of the survival distributions of time to onset of response will be obtained and the survival distributions will be compared using the log-rank test. The survival distribution, $H(t)$, is the probability that onset will occur after time t . Duration is defined as the number of weeks from onset to offset. Offset for a responder is the first week at which the criterion for response is no longer met. The treatment specific survival distributions of duration will similarly be compared using the log-rank test. The null hypothesis for the second primary outcome measure is that there is no difference between the two treatment groups in the proportion of subjects who are responders (defined as a 20% or greater reduction in PSYRATS Delusions Subscale total score) beginning in week two to the end of the treatment phase. The statistical analysis will be based on a repeated measures logistic regression model. The independent terms in the model will include the same variables and covariates used in the MMRM analysis. By the definition of responder, there cannot be any missing data.

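### The missed-visit rule withdraws subjects from the study while another section promises follow-up regardless of compliance, and the plan does not say whether outcome ratings continue

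*Combined protocol and SAP*

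**What the plan says.** Under Methods and Procedures, the CBT/DCS Protocol section sets the attendance rule: "If a subject misses three consecutive study visits and corresponding CBT sessions, he/she will be withdrawn from the study". The reason follows: "These missed visits and sessions may compromise the integrity of the study data and adversely affect the therapeutic alliance". The alliance is described there as important to the CBT.

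The Assessments section sets the follow-up rule: "Participants will be followed regardless of whether they remain on study drug or comply with CBT sessions to permit an unbiased causal estimate", under the intention-to-treat principle. It deals with compliance separately: "a per protocol analysis will be performed using data only from subjects who have substantially complied with the protocol".

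The same section gives the rating schedule. The full battery, which includes the PSYRATS, is given at baseline, weeks 4, 8, 12 and 24, and in most subjects week 36. To this it adds: "In addition, the Delusion Subscale of the PSYRATS will be administered at weeks 2, 3, 6 & 10 to assess the time course". On timing: "Ratings will be performed prior to the DCS/CBT session each week".

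Week 12 is the primary timepoint in the Analysis Plan. Under Missing data, the plan says: "All randomized subjects, both completers and non-completers, will be included in the analysis without imputation". It claims unbiasedness if missing follow-up data are missing at random. The secondary persistence hypothesis in the Specific Aims is that "DCS improvement of delusions compared to placebo will persist at 3 and 6 month follow-up".

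**The concern.** For most non-compliers the two rules agree. A subject who refuses drug or CBT but attends for ratings does not trigger the attendance rule and is simply followed. The difficulty is the subject who misses three weeks of visits and sessions together and could still be rated afterwards. That subject meets the attendance rule, and is also a CBT non-complier whom the Assessments section says will be followed.

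The attendance rule can be read two ways. It speaks of leaving the study rather than leaving treatment, which suggests that ratings end. Its therapeutic-alliance reason, and its place in the section describing the CBT and drug course, suggest a rule about treatment only. No section sets a priority.

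At stake are the later ratings of subjects who disengaged. If the rule ends ratings, the week-12 comparison depends more on missing-at-random for a group in which that assumption is least comfortable. The persistence analysis also loses its follow-up ratings for these subjects.

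**Working it through.** **1. The relevant sections side by side**

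- CBT/DCS Protocol: the trigger is missed visits and sessions together; the consequence is withdrawal from the study; later ratings are not mentioned.
- Assessments: follow-up whatever the drug or CBT compliance, with no stated exception; missed study visits are not mentioned.
- Analysis Plan, Missing data: settles who is analysed, not whether ratings are still collected.
- Protection against Risks: suspends study drug on clinical worsening; follow-up is not mentioned.

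No section limits the first rule to treatment or exempts its withdrawals from the second.

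**2. Ratings lost per affected subject, if the rule ends ratings**

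Assumption: one study visit per weekly session. A run starting at week s covers weeks s, s+1 and s+2, with s from 1 to 10, and the rule fires after week s+2. The PSYRATS Delusions schedule is baseline and weeks 2, 3, 4, 6, 8, 10, 12, 24 and (in most) 36.

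| Weeks missed | Ratings still ahead, lost only to the rule |
|---|---|
| 1–3 | 4, 6, 8, 10, 12, 24, (36) |
| 2–4 and 3–5 | 6, 8, 10, 12, 24, (36) |
| 4–6 and 5–7 | 8, 10, 12, 24, (36) |
| 6–8 and 7–9 | 10, 12, 24, (36) |
| 8–10 and 9–11 | 12, 24, (36) |
| 10–12 | 24, (36) |

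Week 12 is still ahead for s = 1 to 9, which is 9 of 10 runs. Week 24 and any week 36 rating are ahead in all 10.

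For s = 4 to 9, week 3 is not in the missed run, so the subject may already count toward the 60 evaluable, defined by completing the week-3 assessment. Of the five ratings at weeks 4, 6, 8, 10 and 12, runs starting at weeks 4, 5, 6, 7, 8 and 9 keep 0, 1, 1, 2, 2 and 3 with the rule, against at most 3, 4, 3, 4, 3 and 4 without it.

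**3. Power, as a sensitivity calculation only**

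Inputs from Estimation of statistical power and the Analysis Plan: 60 evaluable, 1:1 (30 per arm), standardised effect 0.8, two-sided 0.05, stated power above 85%.

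The noncentrality parameter is 0.8 × √(n/2), with 2n − 2 degrees of freedom.

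- n = 30: 0.8 × √15 = 3.10, power 86.1% (normal approximation 87.3%). The stated figure reproduces.
- n = 29: power 84.9%.

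The documents give no rate of loss after week 3 for this trial. The only retention figure is 93%, from the earlier 16-week CBT trial described under Preliminary study of CBT for delusions. Taking 100% − 93% = 7% as an assumed loss, with lost subjects contributing nothing:

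- 7%: n = 30 × 0.93 = 27.9, 0.8 × √13.95 = 2.99, power 83.5%, a fall of 86.1 − 83.5 = 2.6 points.
- 10%: n = 27, power 82.2%.
- 20%: n = 24, power 77.4%.

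At each assumed rate this is an upper bound on the power loss for a fixed effect of 0.8. The mixed model uses earlier ratings, and some of these subjects would be lost without the rule.

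**The case against.** The strongest reply is that a specific non-attendance rule can coexist with a general compliance rule. The follow-up promise names drug and CBT, not missed visits, and the attendance rule needs both visits and sessions to be missed. This narrows the point to one group of subjects. It does not remove it, because those subjects have also not complied with CBT and no section says which rule gives way.

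It can also be said that the Analysis Plan already includes non-completers. That is true of the analysis set, but it does not supply a week-12 rating that nobody attempted to collect.

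Several stronger readings are tempting, and the documents do not support them:

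- A reader might infer that the data-integrity reason shows the rule is meant to end ratings. The alliance reason and the rule's placement point the other way, and neither reason mentions later ratings.
- A reader might infer that collected data are thrown away or that the intention-to-treat set is broken. Earlier ratings stay in the model; the loss is of ratings not collected.
- A reader might take 9 of 10 as a likelihood. It counts positions in the calendar and says nothing about how many subjects are affected.
- A reader might infer that someone missing weeks 4–6 keeps only ratings taken before the first DCS dose. The timing in Assessments and the dosing from session 3 suggest this, but Estimation of statistical power describes week 3 as the first assessment following study drug. The documents disagree, so nothing here rests on it.
- A reader might infer that withdrawn subjects become non-responders, since the responder definition is said to leave no missing data. The plan does not state this, and the question arises for any missed week-12 rating, whatever its cause.

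**Conclusion.** The concern holds in a narrow form. The plan has two rules that conflict for subjects who miss three consecutive visits and sessions but could later be rated, and it sets no priority between them. If the attendance rule ends ratings, an affected subject loses an obtainable week-12 rating in 9 of 10 possible runs, and week 24 and any week 36 rating in all of them. These counts rest on one visit per weekly session, and each rating ahead is obtainable only if the subject can be reached.

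The frequency of such withdrawals and the resulting bias cannot be derived from the documents. Under the assumed 7% loss the power cost is at most about 2.6 points. The stated power itself is not in dispute. The case for acting is the plan's own intention-to-treat aim and the low cost of meeting it. I would rate it as something that should be fixed, with medium confidence.

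**What to change.** Reconcile the CBT/DCS Protocol and Assessments sections. State that, whatever the sponsor and investigator decide about CBT and study drug, the missed-visit rule does not end outcome assessment. Unless consent is withdrawn, attempt the remaining scheduled PSYRATS Delusions ratings, giving week 12 first priority, and include them in the intention-to-treat mixed model. Handle compliance through the per-protocol analysis already planned.

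The cost is a short wording amendment and extra effort to contact non-attenders for visits already on the schedule. Some will remain unreachable, so not every rating would be recovered.
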